### 3.1.2 Phase 2 Portion – Randomized, Placebo-Controlled

[figure not shown]
The study arms in the phase 2 portion include the following:

- Experimental arm: azacitidine in combination with vadastuximab talirine
- Comparator arm: azacitidine in combination with placebo

Subjects will be randomized in a 1:1 manner to one of the study arms above. Randomization will be stratified by Eastern Cooperative Oncology Group (ECOG) performance status (0 vs 1 or 2) and International Prognostic Scoring System (IPSS) score (Intermediate-2 vs High risk).

Subjects will receive vadastuximab talirine in combination with azacitidine in 28-day cycles, starting at the dose level of vadastuximab talirine determined in phase 1. Response assessments (bone marrow examination and CBC) will be conducted once between Day 22 and Day 29 of even-numbered cycles until CR, then every 4 cycles thereafter. Subjects may continue on study treatment until disease progression, relapse, or unacceptable toxicity. After discontinuation of study treatment, subjects who have not had progression or relapse will continue to be assessed for response every 4 months through 24 months after EOT or until initiation of another anticancer treatment, progression, or relapse, whichever comes first. All subjects will be contacted for survival status every 2 months after EOT in follow up until death or study closure, whichever comes first. Safety will be monitored through the surveillance of AEs, laboratory test measures, physical examination findings, and concomitant medication records. An Independent Data Monitoring Committee (IDMC) (Section 7.2) will also periodically assess the ongoing safety data and make recommendations to either continue evaluating the combination or to stop the study due to toxicity concerns. Figure 2 is a study schematic for the Phase 2 Portion.

**Figure 2: Study Schematic – Phase 2 Portion**

AZA = azacitidine; CR = complete response.

- a Subjects may continue to receive repeated cycles of treatment until disease progression, relapse, unacceptable toxicity, or other discontinuation criteria are met.
- b For subjects who discontinue without having experienced disease progression follow-up will include disease assessment (CBC and bone marrow) every 4 months for 24 months or until disease progression. Subjects will be followed every 2 months for survival until death or the end of the study.

Unblinding a subject’s treatment assignment will be limited to emergency circumstances where knowledge of the treatment assignment would affect decisions regarding the management of the

subject. In the event of such an emergency circumstance, a formal unblinding procedure will be followed to allow the investigator to immediately access a subject's treatment assignment. Information on study treatment assignment should not be distributed to any other personnel involved in the clinical trial.

Please refer to Table 4 of the protocol for the full Schedule of Study Procedures and Assessments, Table 5 for the Schedule of Pharmacokinetic, Immunogenicity, and Biomarker Assessments for the Phase 1 Portion and Table 6 for Schedule of Pharmacokinetic, Immunogenicity, and Biomarker Assessments for the Phase 2 Portion.

### 3.2 Sample Size Considerations

Phase 1 Portion (minimum of 6 subjects per cohort): Six subjects are adequate to appropriately assess the safety profiles and DLT rates of differing dose levels of vadastuximab talirine in combination with azacitidine. If the true incidence rate of DLT is 10%, the probability of considering a dose level tolerable (ie,  $\leq 1$  of 6 subjects experiences a DLT) will be 88.6%. If the true incidence rate of DLT is 50%, the probability of considering a dose level tolerable will be 10.9%.

With this type of study design, the exact number of subjects needed to complete the Phase I Portion is unknown because it depends on the number of cohorts required to reach MTD. Approximately 24 subjects are expected to participate in the Phase 1 portion of this trial, assuming 4 dose-escalation cohorts of 6 subjects.

Phase 2 Portion (106 subjects): A sample size of 106 subjects will provide 85% power to detect a treatment difference in ORR, assuming an ORR of 30% for azacitidine alone vs 55% for the combination vadastuximab talirine with azacitidine, at a 2-sided 0.1 alpha level.

### 3.3 Study Duration

There will be approximately 35 sites enrolling subjects in this study. The estimated duration of study treatment through final primary analysis is approximately 51 months from enrollment of the first subject to completion of the last subject. All subjects will be contacted for survival status every 2 months after EOT in follow up until death or study closure, whichever comes first.

### 3.4 Randomization

During the Phase 2 Portion of the study, subjects will be randomized in a 1:1 manner to azacitidine with vadastuximab talirine and azacitidine with placebo. Randomization will be stratified by ECOG performance status (0 vs 1 or 2) and IPSS score (Intermediate-2 vs High risk).

## 4.0 Study Variables and Covariates

### 4.1 Primary Variable

The primary endpoint of the Phase 1 Portion of the study is to determine the recommended dose for the Phase 2 Portion, based upon the MTD.

The primary efficacy endpoint of the Phase 2 Portion of the study is the ORR, defined as the proportion of subjects who achieve any category of CR (CR and Marrow CR) or PR based on the 2006 International Working Group (IWG) criteria for MDS.

## 4.2 Secondary Variables

### 4.2.1 Efficacy

Secondary efficacy endpoints of the Phase 2 Portion of the study are the following:

- Complete response (CR) rate
- Hematologic improvement (HI) rate
- Duration of response (DOR)
- Progression-free survival (PFS)
- Rate of transformation to AML
- Overall survival (OS)

## 4.3 Other Variables

### 4.3.1 Pharmacokinetic and Antitherapeutic Antibody Assessments

- Estimates of selected PK parameters for plasma vadastuximab talirine and released SGD-1882
- Incidence of ATA

### 4.3.2 Biomarker Assessments

Biomarker assessments may include

- CD33 expression level
- Abundance of MDSC
- Characterization of leukocyte subpopulations in peripheral blood (peripheral blood mononuclear cells; PBMCs)
- Variation in sequence of CD33 and genes commonly mutated in MDS and hematologic malignancies
- Soluble CD33
- Abundance of a variety of cytokines
- Testing for Paroxysmal Nocturnal Hemoglobinuria (PNH) and human leukocyte antigen (HLA)-DR15

### 4.3.3 Safety

Safety assessments for both the Phase 1 Portion and the Phase 2 Portion of the study will consist of the following:

- Surveillance of AEs
- Laboratory test measures
- Physical examination findings
- Concomitant medication records.

#### 4.3.4 Quality of Life

Quality of life for both the Phase 1 Portion and the Phase 2 Portion of the study will be assessed with the Quality of Life Questionnaire (QLQ)-C30 patient reported outcomes (PRO) tool at protocol-defined time points.

#### 4.4 Predetermined Covariates and Prognostic Factors

Randomization will be stratified by ECOG performance status (0 vs 1 or 2) and IPSS score (Intermediate-2 vs High risk) to ensure some level of balance between treatment arms and these stratification factors will be used as covariates in statistical models for the primary analysis.

## 5.0 Definitions

**Absolute Dose Intensity (ADI):** is defined as the actual dose ( $\mu\text{g}/\text{kg}$ ) per unit of time that the subject received over the entire treatment period. Actual time for the denominator will be calculated separately for vadastuximab talirine and azacitidine as follows:

Vadastuximab talirine: last day 1 dose date of azacitidine where vadastuximab talirine was received in that cycle +28 - first dose of any study drug

Azacitidine: last day 1 dose date of azacitidine +28 - first dose of any study drug

**AEs Leading to Discontinuation of Study Drugs:** are those indicated by “Reason for discontinuing treatment” of AE (linked by AE number) on the End of Treatment Summary page of the CRF.

**Age (years):** will be calculated with the SAS INTCK function using informed consent date and birth date.

**ATA Incidence Rate:** is defined as the proportion of patients that develop ATA at any time during the study.

**Baseline:** is defined as the most recent measurement prior to the first dose of any study treatment unless otherwise defined in a specific section of the SAP.

**Complete Response:** is defined as an answer of “Complete Remission” for the question “Response Assessment” in CRF form of “Response Assessment”.

**Concomitant Medication:** is defined as any medication ongoing at the start of vadastuximab talirine or Placebo dosing or with a start date on or after the first dose date of any study treatment dose date up to 30 days post last dose or EOT whichever is longer. Medications with start and end dates before the first dose date of any study treatment may be concomitant if the medication is marked as ongoing. For medications with missing or partial start dates, a missing start date will be imputed with the first dose date of any study treatment, missing month and day for a partial start date will be imputed with January 1st, and missing day for a partial start date will be imputed with the first day of the month.

**Days:** The following unit conversion will be implemented unless otherwise specified:

$$\text{Months} = \text{Days} / 30.4375$$

$$\text{Years} = \text{Days} / 365.25.$$

**Deaths:** Subject deaths will be determined from End of Study CRF page (where reason for discontinuation is death) and from AE CRF page (where CTCAE grade is 5 or outcome is “fatal”) and from the follow-up CRF page (where the answer to the question “Is the patient alive?” is “No”). The number of days between vadastuximab talirine or placebo last dose and death will be calculated as (date of death – last vadastuximab talirine or placebo dose date + 1).

**Dose-Limiting Toxicity:** see [Section 3.1.1](#).

**DLT Evaluable Subject:** is defined as all Phase 1 subjects who have completed at least Cycle 1 of treatment (Cycle 1 of treatment is completed when the patient receives the first dose of azacitidine on Day 1 of Cycle 2), or discontinued study treatment because of AEs or for a safety-related reason (defined as AE, Investigator Decision, or Progressive Disease) before having had

the opportunity to receive the first dose of azacitidine on Day 1 of Cycle 2, or who experienced a DLT.

**Duration of Response:** is defined as the time from first observation of response (PR+CR/Marrow CR) to disease progression/relapse or death from any cause, whichever occurs first.

**Duration of Treatment:** is defined as time from the first dose of any study drug until 28 days after the last day 1 dose date, or until : last contact date if the patient is still on treatment at the time of the analysis.

Minimum(Last day 1 dose date + 27, death date, last contact date) – first dose date +1

**Infusion Related Reactions AE:** is defined for those AEs that have responses of “Yes” for the question “Were there any infusion-related reactions?” in the CRF forms “Treatment – Blinded Study Drug”, “Treatment – Azacitidine”, or “Treatment – Vadastuximab Talirine”.

**Hematologic Improvement:** is defined in [Table 1](#)

**Hematologic Improvement (HI) Rate:** is defined in as the proportion of subjects with Erythroid response, Platelet response or Neutrophil response as defined in [Table 1](#).

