9.5.1.4.3 Dose Modifications

Common toxicities including myelosuppression, nausea, gastrointestinal toxicity, fatigue, pyrexia, headache, weight decrease, dyspnea, rash, and stomatitis should be managed according to institutional standards or accepted guidelines (eg, American Society of Clinical Oncology [ASCO] guidelines for the use of WBC growth factors [26]). Growth factor support may be administered as needed according to institutional standard of care.

Vadastuximab Talirine

[Table 2](#) describes guidelines for dose modifications of vadastuximab talirine (Phase 1 Portion) or blinded study treatment (Phase 2 Portion) for toxicity.

Dose delays of any study treatment are permitted. If dosing is delayed for azacitidine, vadastuximab talirine (Phase 1 Portion), or blinded study treatment (Phase 2 Portion), both study treatments should be held and resumed together on the same schedule except when one agent is omitted during a cycle due to toxicity.

For patients who achieve a response to therapy, dose decreases, delays, or dose re-escalation (to original dose level) are permitted at the discretion of the medical monitor and site Investigator. Following achievement of marrow blast clearance to $<5\%$ (ie, a CR or marrow CR), patients originally treated with a dose higher than 5 mcg/kg of study drug will receive azacitidine with vadastuximab talirine (Phase 1 Portion) or blinded study treatment (Phase 2 Portion) as continuation therapy at the maintenance dose of 5 mcg/kg in subsequent cycles.

Azacitidine, vadastuximab talirine (Phase 1 Portion), or blinded study drug (Phase 2 Portion) may be permanently discontinued in the event of unacceptable related toxicity. Subjects will not be considered off study treatment until both study treatments are discontinued.

If subjects become candidates for stem cell transplant after enrollment, vadastuximab talirine must be discontinued at least 30 days prior to initiation of preparative regimen for stem cell transplant.

Table 2: Dose Modifications for Vadastuximab Talirine-Associated Toxicity

Category	Event	Action

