Hematologic toxicity with marrow blast count <5% ^a	≥ Grade 3 neutropenia or thrombocytopenia	Cycles of treatment may be delayed up to 14 days ^b until hematologic recovery is observed. Adequate hematologic recovery is defined as neutropenia and thrombocytopenia improved to < grade 3 (unsupported), OR ANC / platelets ≥ [(NADIR COUNT ^c) + (BASELINE COUNT ^d – NADIR COUNT) x 0.50] If hematologic recovery as defined above has not occurred within 14 days of the end of the cycle (by Day 42), omit vadastuximab talirine (Phase 1) or blinded study treatment (Phase 2) from the next cycle, and initiate next dose of azacitidine based on marrow cellularity as defined in Table 3.
Hematologic toxicity with marrow blasts ≥5% ^b	≥ Grade 3 neutropenia or thrombocytopenia	Treatment may continue without dose modification.
Clinically significant non-hematologic toxicity or asymptomatic non-hematologic laboratory abnormality (with the exception of hepatic toxicity)	≥ Grade 3 event	Treatment delay of up to 14 days is permitted until resolution of toxicity to < grade 3.
Laboratory evidence of hepatic toxicity (elevation in ALT, AST, or total bilirubin)	≥ Grade 3 event	Treatment delay of up to 14 days is required until resolution of toxicity to ≤ grade 1 or baseline. If toxicity has not resolved within 14 days, permanently discontinue vadastuximab talirine (Phase 1) or blinded study treatment (Phase 2)

ALT = alanine aminotransferase; ANC = absolute neutrophil count; AST = aspartate aminotransferase.

- a If cytopenias above grade 3 (e.g., ANC <1000/mm³ or platelets <50 x 10⁹/L) are present at Day 28 of a cycle in which no response assessment is required, an ‘unscheduled’ bone marrow biopsy is required within 14 days of the scheduled end of the cycle (eg, between Day 28 and Day 42). If the bone marrow cellularity is ≤10%, vadastuximab talirine or blinded study treatment will be permanently discontinued. If marrow cellularity is >10%, follow guidance as above.
- b Delays of >14 days may be permitted with approval of the medical monitor.
- c Nadir Count = the lowest count reached during the treatment cycle.
- d Baseline Count = counts prior to Cycle 1 of study treatment.

Azacitidine

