**Progression-Free Survival:** PFS is defined as the time from first dose of study medication to first documentation of disease progression/relapse, or to death due to any cause, whichever occurs first. For subjects without disease progression/relapse or death on study, PFS will be censored at the time of the last on-study disease assessment demonstrating a lack of disease progression/relapse. If more than one date of progression is available, the earliest date will be used to determine PFS. Subjects who receive another antineoplastic therapy in the absence of documented progression will be censored at the time of receiving off-protocol therapy for

malignancy, EXCEPT that subjects who receive stem cell transplant in remission will continue to be followed for progression.

**Relative Dose Intensity (RDI):** is defined as the absolute dose intensity over the intended dose intensity,

$$\text{RDI} = \text{ADI} / \text{IDI} * 100.$$

Where IDI (intended dose intensity) is defined as the intended dose of drug (mg/kg) per unit of time.

**Study Drug:** The study drug is vadastuximab talirine (SGN-CD33A) for the study.

**Serious AE (SAE):** is defined as an answer of “Yes” for the question “Was this Serious” in CRF form of “Adverse Events and Pre-Existing Conditions”.

**Time Since Initial Diagnosis:** is defined as

Date of first dose – date of initial MDS diagnosis + 1.

**Transformation to AML:** is defined as an answer of “Yes” for the question “Has the patient progressed to AML” in CRF form of “Follow-Up”.

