#### Phase 2 Portion Exposure

During the Phase 2 Portion of the study, subjects will be randomized to receive either vadastuximab talirine administered every 4 weeks (after azacitidine on the last day of azacitidine administration) via IV push at the dose determined in the Phase 1 Portion or placebo every 4 weeks (after azacitidine on the last day of azacitidine administration) via IV push.

All subjects will also receive azacitidine 75 mg/m^2 SC or IV (at the investigator's discretion) for 7 days (7 consecutive days or 5 days on/2 days off/2 days on), beginning on Day 1 of repeated 4-week cycles.

Treatment administration of both vadastuximab talirine and azacitidine will be summarized for both study phases by dose level using the safety set. The number and percentage of subjects whose dose was ever modified will be summarized by modification type, cycle and overall (i.e. over all drug administrations for a subject). Summary statistics related to duration of treatment and compliance will be presented as detailed below. For the continuous parameters, the mean, SD, median, minimum and maximum will be presented. The following summary statistics related to drug exposure will be calculated by dose level:

The number and percentage of subjects with at least 1 dose delayed, the number of doses delayed, at least 1 dose reduced, the number of doses reduced, the number of subjects with at least 1 dose unplanned adjustment and reasons for unplanned adjustment, and number of unplanned dose adjustments, the number of subjects with at least one infusion-related reaction, the number of infusion-related reactions, the number of subjects with a delayed hypersensitivity reaction, the number of delayed hypersensitivity reactions, the duration of treatment (weeks), the

number of doses received, the number of treatment cycles received (continuous summary), the number of subjects receiving 1, 2, 3, etc. cycles, the cumulative dose administered ( $\mu\text{g}/\text{kg}$  and total  $\mu\text{g}$ ), the average dose per cycle ( $\mu\text{g}/\text{kg}$  and  $\mu\text{g}$ ), absolute dose intensity ( $\mu\text{g}/\text{kg}$ ), and relative dose intensity (%) will be presented.

A listing of intended dose regimen, intended dose, actual dose administered, and reasons for dose delayed, dose reduced, dose adjustment, and/or infusion-related reactions will be displayed.

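### The vadastuximab dose-intensity denominator does not match its own stated time basis, and vadastuximab-only cycles at the end of treatment push RDI above 100%

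*SAP*

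**What the plan says.** SAP section 5.0 (Absolute Dose Intensity, ADI) defines ADI as the actual dose "per unit of time that the subject received over the entire treatment period". It then gives each drug its own denominator. For vadastuximab talirine this is "last day 1 dose date of azacitidine where vadastuximab talirine was received in that cycle +28 - first dose of any study drug". The parallel rule is "Azacitidine: last day 1 dose date of azacitidine +28 - first dose of any study drug". So each clock stops with that drug's own last cycle, and both are measured from azacitidine Day 1 dates.

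RDI, in the same section, "is defined as the absolute dose intensity over the intended dose intensity", times 100. SAP 9.3.1 (Extent of Study Drug Exposure) lists a series of exposure summaries, at the end of which "relative dose intensity (%) will be presented".

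Protocol 9.5.1.4.3 (Dose Modifications) separates the two agents. Either may be permanently stopped for toxicity, and "Subjects will not be considered off study treatment until both study treatments are discontinued". Table 2 there says to "omit vadastuximab talirine (Phase 1) or blinded study treatment (Phase 2) from the next cycle" when counts have not recovered by Day 42. It also stops vadastuximab permanently for marrow cellularity of 10% or less, or for hepatic toxicity that has not resolved within 14 days. Protocol 10.2.2 describes Phase 2 cycles as azacitidine and/or blinded medication. Single-agent cycles of both kinds are therefore possible within the treatment period.

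**The concern.** The formula and the sentence that introduces it describe different quantities. The sentence promises a rate over all time on treatment. The formula stops when vadastuximab stops, although under the protocol the subject may still be on study treatment.

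There is also a mechanical fault. A cycle in which vadastuximab is given without azacitidine has no azacitidine Day 1 dose date, so it cannot move the end of the denominator. Its dose still enters the numerator. If such cycles come last, RDI rises above 100% for a subject who never received more than the planned dose.

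What is at stake is how the exposure tables are read. One table could show a subject with about 24 weeks of treatment (the SAP's Duration of Treatment carries no vadastuximab condition), two vadastuximab doses and a vadastuximab RDI of 100%, with nothing to say that the RDI covers only the first 8 weeks.

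**Working it through.** The documents state no ADI or RDI value, so there is no figure of the plan's own to reproduce. The check applies the formula to illustrative courses.

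**Inputs.** 28-day cycles with one vadastuximab dose each (SAP 3.1.1), and the SAP 5.0 denominators. Assumptions: six cycles, full dose D whenever given, and intended dose intensity of D per 28 days. D cancels.

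**Formulas.**
- SAP RDI = (number of doses × 28) / (start of last cycle with both drugs + 28 − first dose) × 100.
- Whole-period RDI = (number of doses × 28) / (start of last cycle with either drug + 28 − first dose) × 100.

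In the table, B is a cycle with both drugs, A is azacitidine only and V is vadastuximab only.

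| Course | Doses | SAP days | SAP RDI | Whole-period days | Whole-period RDI |
|---|---|---|---|---|---|
| BBBBBB | 6 | 168 | 100% | 168 | 100% |
| BAAAAA | 1 | 28 | 100% | 168 | 16.7% |
| BBAAAA | 2 | 56 | 100% | 168 | 33.3% |
| BBBAAA | 3 | 84 | 100% | 168 | 50.0% |
| BBABBB | 5 | 168 | 83.3% | 168 | 83.3% |
| BABABA | 3 | 140 | 60.0% | 168 | 50.0% |
| BBBBVV | 6 | 112 | 150% | 168 | 100% |
| BBBVVV | 6 | 84 | 200% | 168 | 100% |
| BBBBVB | 6 | 168 | 100% | 168 | 100% |

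The regular course (BBBBBB) comes out right, so the formula fails only in particular patterns.

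**Azacitidine-only cycles at the end.** BBAAAA gives 2 × 28 / 56 = 100%, against 2 × 28 / 168 = 33.3%. A delay just before those cycles is lost as well. With one dose in Cycle 1, a 14-day delay and then five azacitidine-only cycles, the SAP denominator is 28 days (100%). The whole period is 154 + 28 = 182 days (28 / 182 = 15.4%).

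**What the formula does count.** A gap followed by a combined cycle lowers RDI correctly (BBABBB). So do delays before the last vadastuximab cycle: with 42-day cycles, BBAAAA gives 56 / (42 + 28) = 80.0%, against 56 / (210 + 28) = 23.5%. RDI is exactly 100% after early stopping only if every earlier dose was full and on time.

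**Vadastuximab-only cycles at the end.** BBBBVV gives 6 × 28 / 112 = 150%. If the clock ended at vadastuximab's own last cycle, whichever drug marked its start, the denominator would be 140 + 28 = 168 days and RDI 100%. The excess therefore comes from the azacitidine anchor, not from choosing an on-drug measure. A later combined cycle removes it (BBBBVB).

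**The azacitidine rule.** In BBBBVV the azacitidine denominator is also 112 days, so azacitidine RDI is 4 × 28 / 112 = 100%, against 4 × 28 / 168 = 66.7% over the whole period. The mismatch with the stated time basis applies to both drugs.

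**The case against.** The strongest reply is that an on-drug measure was intended. Straight after the whole-period phrase, the SAP says the time is calculated separately for the two drugs and gives two parallel rules, each ending with that drug's own last cycle. That looks deliberate. A whole-period figure also has a weakness: two full doses followed by azacitidine to Cycle 6 give 33.3%, but to Cycle 20 they give 2/20 = 10%, with identical vadastuximab exposure. This stands. Replacing one definition with the other is partly a preference, and what remains of the first problem is a wrong or missing label.

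A reader might go further and infer that the SAP hides permanent discontinuation. It does not. Protocol 13.6.7 and SAP 9.3.1 also call for doses received, cycles received and cumulative dose, where a subject with two vadastuximab doses is plain to see. A reader might also infer that the worst-tolerated dose level could show the highest RDI. The documents give no basis for expecting this, because delays, reductions and gaps before the last vadastuximab cycle still lower RDI.

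On RDI above 100%, the reply is that vadastuximab-only cycles should be rare. The protocol times vadastuximab to the last azacitidine day and sets out no schedule for giving it alone, and Table 2 never drops azacitidine alone. That is fair as to frequency. But protocol 9.5.1.4.3 and 10.2.2 do allow the pattern, and the on-drug reading does not explain the result.

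**Conclusion.** The point holds as a minor correction. The vadastuximab denominator contradicts the time basis stated in its own definition, and the azacitidine denominator does so in the same way. For full, on-time doses stopped after Cycle 1, 2 or 3 of 6, the formula gives 100%, where the stated basis gives 16.7%, 33.3% or 50.0%. Separately, vadastuximab-only cycles at the end of treatment produce an RDI above 100% whichever measure was meant: 150% or 200% in the two six-cycle examples.

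These are constructed courses, not expected values. The documents do not say how often either pattern would occur. The effect is confined to descriptive exposure tables. The primary ORR comparison does not use RDI, and neither document names it as an input to the Safety Monitoring Committee's DLT-based dose recommendation.

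**What to change.** 1. In SAP 5.0, anchor the vadastuximab denominator to the start date of the last cycle in which vadastuximab was given, not to an azacitidine dose date. If no azacitidine was given and the CRF holds no cycle start date, derive one from the vadastuximab dose date by a rule written into the SAP. The CRF is not among the documents, so whether that date is collected needs checking.
2. Then choose one of two courses:
   - label the measures for both drugs as RDI while on that drug, and add a whole-period RDI beside them (start of the last cycle with either agent + 28 − first dose); or
   - keep only the on-drug measures and remove the whole-period phrase from the ADI definition.
3. In the same edit, align the units. Intended dose intensity "is defined as the intended dose of drug (mg/kg) per unit of time", while ADI is in µg/kg.

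With step 1, the BBBBVV course reads 100%. With the first option in step 2, the BBAAAA course reads 100% on drug and 33.3% over the whole period. The cost is a revised definition and, under the first option, one more table row and a whole-period figure that depends on how long the other agent continues.

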10.2.2 Phase 2 Portion

The subject will receive treatment in repeated 28-day cycles of azacitidine (75 mg/m² SC or IV for 7 consecutive days or 5 days on/2 days off/2 days on) and/or blinded study medication (vadastuximab talirine or placebo; [Section 9.5.1](#)). In addition, procedures will be performed as indicated below.

10.2.2.1 Cycle 1

- Day 1, pretreatment:
 - Biomarker assessments ([Section 11.4](#))
 - Whole blood (sCD33 - cytokines and research; MDSC; CD33 expression; and PBMCs)
 - ECOG performance status and weight ([Section 11.5](#))
 - Clinical laboratory tests (CBC with differential and serum chemistry including ferritin; [Section 11.7](#))
 - PRO questionnaire ([Section 11.9](#))
 - Blood samples for ATAs (within 24 hours before beginning the azacitidine infusion; [Section 11.8](#))
- Days 1 to 6 (if azacitidine is administered on 7 consecutive days) or Days 1 to 5, and 8 (if administered 5 days on/2 days off/2 days on): Administer azacitidine according to the selected treatment schedule ([Section 9.5.1.3](#))
- Day 7 (if azacitidine is administered on 7 consecutive days) or Day 9 (if administered 5 days on/2 days off/2 days on), pretreatment:
 - PK sample collection (within 8 hours before beginning the blinded study medication) ([Section 11.4.1](#))
 - Biomarker assessments ([Section 11.4](#))
 - Whole blood (sCD33 - cytokines and research; MDSC; CD33 expression; and PBMCs)
 - Vital signs
 - After completion of pretreatment procedures, administer azacitidine ([Section 9.5.1.3](#)) followed by blinded study medication ([Section 9.5.1.2](#))
 - Vital signs (within 30 minutes after completing the blinded study medication infusion)
 - PK sample collection (within 15 minutes after completing the blinded study medication infusion; [Section 11.4.1](#))
- Day 15 (± 1 day):

- Clinical laboratory tests (CBC with differential, serum chemistry including ferritin, and urinalysis; [Section 11.7](#))

10.2.2.2 Cycle 2

- Day 1 (± 1 day), pretreatment:
 - ECOG performance status and weight ([Section 11.5](#))
 - PRO questionnaire ([Section 11.9](#))
 - Clinical laboratory tests (CBC with differential, serum chemistry including ferritin, and urinalysis; [Section 11.7](#))
 - Serology laboratory tests (inflammatory serologies; [Section 11.7](#))
 - Blood samples for ATAs (within 24 hours before beginning the azacitidine infusion; [Section 11.8](#))

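### The SAP's vadastuximab dose intensity is an unlabelled on-drug measure: it stays near 100% after a permanent stop and can exceed 100% if azacitidine alone is stopped

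*SAP*

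**What the plan says.** SAP 5.0 defines absolute dose intensity (ADI) as the actual dose "per unit of time that the subject received over the entire treatment period". It then says that the denominator is calculated separately for each drug. For vadastuximab it is "last day 1 dose date of azacitidine where vadastuximab talirine was received in that cycle +28 - first dose of any study drug". For azacitidine it runs to 28 days after the last azacitidine Day 1. RDI is ADI divided by the intended dose intensity (IDI), times 100. The SAP's Duration of Treatment is a separate variable, the "time from the first dose of any study drug until 28 days after the last day 1 dose date", with no link to whether vadastuximab was given in that cycle.

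Protocol 9.5.1.4.3 creates the path on which these periods part. Under Table 2, footnote a, if the biopsy for persistent cytopenia shows marrow cellularity of 10% or less, "vadastuximab talirine or blinded study treatment will be permanently discontinued". For hepatic laboratory toxicity of grade 3 or higher the table says: "If toxicity has not resolved within 14 days, permanently discontinue vadastuximab talirine (Phase 1) or blinded study treatment (Phase 2"). Neither rule stops azacitidine, and Table 3 gives timing for the next azacitidine cycle even at cellularity below 15%. The same section adds: "Subjects will not be considered off study treatment until both study treatments are discontinued". Protocol 10.2.2 describes Phase 2 cycles as azacitidine "and/or blinded study medication (vadastuximab talirine or placebo"), so either drug may be given without the other.

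Protocol 13.6.7 asks for exposure, including RDI, separately for the two drugs. SAP 9.3.1 presents it by dose level.

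**The concern.** The words and the formula describe different quantities. The words promise dose delivered over all the time on treatment, while the formula gives dose delivered up to the last vadastuximab cycle. A programmer will follow the formula, and a reader of the table will assume the words.

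The two differ for subjects whose tolerability is of most interest, those taken off the investigational drug for toxicity while azacitidine goes on. Safety of the combination is a secondary objective in both portions. By SAP 7.1 the DLT period ends when azacitidine starts in Cycle 2, so later stops have to be read from the exposure and discontinuation tables. An RDI that does not fall after such a stop can mislead there. The order can also look wrong: a subject who misses one dose and resumes scores below one who is stopped for good after a single dose.

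**Working it through.** The plan states no RDI value, so there is no figure to reproduce. I applied its formulas directly.

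**Inputs.** One vadastuximab dose *d* per 28-day cycle (SAP 9.3.1). ADI, its denominators and RDI as in SAP 5.0. IDI is taken as *d*/28; the SAP does not state the time unit, and it writes IDI in mg/kg but ADI in µg/kg, so I assume one common unit. Worked cases use full doses, no delays, no step-down after response, and six cycles, because the ORR analysis is timed by completion of six cycles (Protocol 13.6.4).

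**Whole period.** Day 1 of Cycle 6 falls 5 × 28 = 140 days after first dose. Adding 28 gives 168 days. The SAP's Duration of Treatment formula agrees: 140 + 27 + 1 = 168.

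**Vadastuximab stopped for good after cycle *m*, azacitidine through Cycle 6.**
- As written: denominator = 28(*m* − 1) + 28 = 28*m*; ADI = *md*/28*m* = *d*/28; RDI = 100% for every *m*.
- Whole period: ADI = *md*/168; RDI = 100 × *m*/6.

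| Vadastuximab given | RDI as written | RDI over whole period |
|---|---|---|
| Cycle 1 only | 28-day denominator: 100% | 1/6 = 16.7% |
| Cycles 1–2 | 56 days: 100% | 2/6 = 33.3% |
| Cycles 1–3 | 84 days: 100% | 3/6 = 50.0% |
| Cycles 1 and 3, then stopped | 84 days: 2/3 = 66.7% | 2/6 = 33.3% |
| Cycle 2 omitted, resumed to Cycle 6 | 168 days: 5/6 = 83.3% | 5/6 = 83.3% |

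The last two rows show the limit of the problem. Omissions before the last vadastuximab dose still lower RDI as written. Only time after that dose drops out.

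**Azacitidine stopped after cycle *k*, vadastuximab through Cycle 6.** The last azacitidine Day 1 in a cycle with vadastuximab is that of cycle *k*, so the denominator stays at 28*k* while six doses accumulate: RDI = 100 × (6*d*/28*k*)/(*d*/28) = 100 × 6/*k*. This is 120% for *k* = 5, 200% for *k* = 3 and 300% for *k* = 2. With the clock tied to the last vadastuximab cycle the denominator is 168 days and RDI is 100%.

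**Behaviour of a whole-period measure.** For a single Cycle 1 dose it gives 50.0%, 25.0%, 16.7%, 12.5% and 8.3% when treatment lasts 2, 4, 6, 8 and 12 cycles. If both drugs stop after one cycle, the denominator is 28 days and RDI is 100% under either definition.

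**The case against.** The strongest reply is that the per-drug clock is deliberate. The SAP announces separate denominators and spells them out, and the protocol asks for exposure by drug. Intensity while on drug is a legitimate measure, and Duration of Treatment need not share its end date. This stands: what is missing is a label that agrees with the formula.

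Second, the whole-period alternative has faults of its own. It still gives 100% when both drugs stop after one dose, and it falls as azacitidine continues for longer, so longer benefit from azacitidine would look like poorer vadastuximab delivery. This also stands, and it is why the whole-period figure should sit beside the current measure rather than replace it.

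Third, a reader might infer that toxicity stops vanish from the report. The documents do not support that. SAP 9.3.1 also presents number of doses, number of cycles, subjects receiving 1, 2, 3 or more cycles, cumulative dose and dose modifications. A one-dose subject is visible there.

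Fourth, a reader might infer that the adverse-event tables would also miss these stops, because SAP 5.0 takes events leading to discontinuation from the reason recorded "on the End of Treatment Summary page of the CRF" and a subject is off treatment only when both drugs have stopped. That depends on how the CRF page is laid out, which these documents do not show, so I draw no conclusion from it.

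Fifth, the case above 100% is marginal. Vadastuximab is scheduled after the last azacitidine dose and no vadastuximab-only schedule is written, although stopping azacitidine alone is permitted.

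**Conclusion.** The concern holds as a mismatch between a definition and its formula. For a subject permanently taken off vadastuximab while azacitidine continues, RDI as written is 100% if the doses given were full and on schedule. Over six cycles the whole-period value is 16.7%, 33.3% or 50.0% after one, two or three doses. Delays, omissions or reductions before the last vadastuximab dose would bring the written figure below 100%. Tying the clock to azacitidine dates is a separate flaw: it produces values above 100% on a permitted but uncommon path whose frequency the documents do not give.

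It would be tempting to convert this into a stated overstatement of mean RDI for an arm or dose level. The documents give no rate of vadastuximab-only stops, so no group-level figure can be supported.

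The scope is descriptive exposure tables only. The DLT rule, the ORR test, alpha and power are untouched. Severity is minor.

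**What to change.** 1. In SAP 5.0, label the current measure *dose intensity while on vadastuximab/blinded drug*. End its clock 28 days after Day 1 of the last cycle in which that drug was given, whether or not azacitidine was given in that cycle. This removes the values above 100% that come from the azacitidine dates.
2. Add a second row, RDI over the whole treatment period, with denominator Day 1 of the last cycle of either drug + 28 − first dose of any study drug. Footnote that it also depends on how long azacitidine continued.
3. In SAP 9.3.1, add the number and percent of subjects whose vadastuximab or blinded drug was permanently stopped while azacitidine continued. This count shows the stops directly, which neither RDI does reliably.

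The cost is SAP wording and table programming. Administration of both drugs is already recorded in the eCRF (Protocol 9.5.4), so no patients, visits or procedures are added.
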